5.9. Study Aims, Hypothesis, Rationale

5.9.1. Aims. The proposed study has two specific aims: **Aim 1.** To compare the two study conditions in terms of: a) XR-NTX treatment adherence; b) opioid use; c) criminal activity; d) re-arrest; e) re-incarceration; and f) HIV risk-behaviors (i. needle use; ii. risky sexual behaviors). **Aim 2.** To determine if the number of months of post-release XR-NTX treatment is related to outcome (a-f above), and if so, is there a point at which XR-NTX v. Non-XR-NTX equilibrates.

5.9.2. Hypothesis. Based on data from the research team's current studies (see above), It is anticipated that the XR-NTX+MMTx condition will have superior outcomes compared to the XR-NTX+OTx condition in terms of outcomes (a)-(f).

5.9.3. Rationale. We are not aware of RCTs using mobile medical treatment for the provision of XR-NTX. However, based on studies utilizing mobile treatment for HIV services, and methadone, which increased access, engagement, and retention, we believe the provision of medical treatment, provided at a participant's place of residence, is expected to yield better adherence, subsequently, improving outcomes mentioned above. If we find a point of equilibration it will tell us how many months we will need to provide mobile treatment (XR-NTX) and at what point it impacts on outcomes-significant given the cost of the medication. It is difficult to provide firm conjectures on this latter question given the lack of research in this area.

Figure 2: Data Collection Schedule

Measures	Source	Interval	Operational Definition
Aim 1: Outcomes (a)-(f)			
a. XR-NTX adherence	Clinic records	B, 1-6	• # of injections due/completed
b. opioid use	ASI/TLFB/UDS	B, 1-6, 7, 12	• days of opioid use • positive opioid urine drug screen
c. criminal activity	ASI/TLFB	B, 1-6, 7,12	• days of crime
d. re-arrest	Official records	12	• time to re-arrest
e. re-incarceration	Official records	12	• time to re-incarceration
f. HIV risk behaviors	RAB/TLFB	B, 1-6, 7,12	• scored 0-22 (higher risk) • scored 0-18 (higher risk)
i. needle use			
ii. risky sex behaviors			
Aim 2: Outcomes (a)-(f)			
(a)-(f) equilibrates	Above	1-6,12	Time to relapse
Supplementary			
other treatment	ASI	B, 1-6, 7, 12	• Days in other treatment
opioid overdose	OOS	B, 1-6, 7, 12	• # of times overdosed
opioid craving	VAS	B, 1-6, 7, 12	• 0-100 (higher cravings)
Quality of Life	QOL	B, 1-6, 7, 12	

Figure 3: Biometric Measures

Measures	Data Collection Point						
	Baseline in prison	1mo	2mo	3mo	4mo	5mo	6/7mo
Biometric Measures (for inclusion/exclusion criteria, patient monitoring and AE determination)							
History & Physical	✓						✓ (7only)
Liver Function Tests, Hepatitis Profile	✓						✓ (7only)
Vital signs	✓	✓	✓	✓	✓	✓	✓
Concomitant medication	✓	✓	✓	✓	✓	✓	✓
Pregnancy	✓	✓	✓	✓	✓	✓	✓
HIV	✓						✓ (7only)
Urine toxicology	✓	✓	✓	✓	✓	✓	✓
Adverse Events	✓	✓	✓	✓	✓	✓	✓

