Objectives/Outcomes:	Aim 1. To compare the two study conditions in terms of: a) XR-NTX treatment adherence; b) opioid use; c) criminal activity; d) re-arrest; e) re-incarceration; and f) HIV risk-behaviors (i. needle use; and ii. risky sexual behaviors). Aim 2. To determine if the number of months of post-release XR-NTX treatment is related to outcomes (a-f above), and if so, is there a point at which XR-NTX v. Non-XR-NTX equilibrates. Such a finding could be potentially important because it would be informative about the needed length of XR-NTX treatment
Study Design:	The study is a parallel two-group randomized controlled trial in which 240 (120 per condition) incarcerated men and women will be randomly assigned within gender to one of two conditions: Condition 1. XR-NTX-OTx. One injection of XR-NTX in prison, followed by 6 monthly injections post-release at a community opioid treatment program. Condition 2. XR-NTX+ MMTx. One injection of XR-NTX in prison followed by 6 monthly injections post-release at the participant's place of residence utilizing mobile medical treatment. All participants will be evaluated at 1-, 2-, 3-, 4-, 5-, 6-, 7- (safety visit) and 12-months after release from prison.

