Subjects:	Inclusion Criteria: (1) adult male or female inmate at BCF, DRCF, BCCC, MCIW CMCF, MCTC, or RCI and be eligible for release within 30 days; (2) history of opiate disorder [meeting DSM-5 criteria of dependence at the time of incarceration; individuals who do not meet criteria at time of incarceration and become addicted during incarceration will be eligible]. Inmates not meeting the opioid-dependence criterion will be eligible if they were treated in an opioid agonist treatment program during the year before incarceration (3) suitability for XR-NTX treatment as determined by medical evaluation; (4) currently opioid-free by history, with negative urine for all opioids and no signs of opiate withdrawal; (5) willingness to enroll in XR-NTX treatment in prison [not currently in or planning to pursue agonist (methadone, buprenorphine) treatment at release]; and (6) planning to live in Baltimore City or County (individuals planning to live outside of Baltimore City/county will be allowed to participate as long as they agree to travel to the treatment clinic if randomized to OTX. Exclusion Criteria: (1) Liver function test levels greater than three times normal (if a blood sample is not obtained at baseline participants will still be eligible for participation); (2) Active medical illness that may make participation hazardous (e.g., unstable diabetes, heart disease). Adequately treated medical conditions are acceptable; (3) Untreated psychiatric disorder that may make participation hazardous (e.g., untreated psychosis, bipolar disorder with mania). Adequately treated psychiatric disorders and appropriate psychotropic medications will be allowed; (4) History of allergic reaction to XR-NTX; (5) Current chronic pain diagnosis for which opioids are prescribed; (6) creatinine above normal limits; (7) pregnancy (for women); (8) Breast-feeding (for women); (9) suicidal ideation (within the past 6-months); and (10) Body Mass Index (BMI) > 40
Study Product:	Vivitrol ® (naltrexone for extended release injectable suspension) 380 mg per month delivered in monthly intramuscular injections
Duration:	7 months (1 injection in prison and 6 in the community.
Sample Size:	240 subjects
Statistical Methodology:	A Generalized Linear Mixed Model (GLiMM) will be used to conduct all analyses.

List of Abbreviations

Abbreviation/specialist term	Explanation
XR-NTx	Long acting naltrexone
DSM-V	Diagnostic and Statistical Manual of Mental Disorders, Fifth Edition

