1.2. Specific Aims

Aim1. To compare the two study conditions in terms of: (a) XR-NTX treatment adherence; (b) opioid use; (c) criminal activity; (d) re-arrest; (e) re-incarceration; and (f) HIV risk-behaviors (i. needle use; and ii. risky sexual behaviors).

Aim 2. To determine if the number of months of post-release XR-NTX treatment is related to outcomes (a)-(f), and if so, is there a point at which XR-NTX v. Non-XR-NTX equilibrates. Such a finding could be potentially important because it would be informative about the needed length of XR-NTX treatment.

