3.0. INNOVATION

The proposed study is innovative because it would be the first randomized controlled trial (RCT) in the US assessing effectiveness of receiving XR-NTX using medical mobile treatment compared to XR-NTX at an opioid treatment program. The public health impact of the proposed study will be highly significant and far-reaching because most individuals with OUDs do not receive treatment while incarcerated, thereby substantially raising their likelihood of re-addiction, overdose death, HIV/AIDS infection, and re-incarceration following release. Furthermore, many individuals in the criminal justice system drop out of treatment; therefore, offering opportunities to improve adherence by attempting to: 1) expand capacity; and 2) implement access by providing treatment at their place of residence may positively impact outcomes. The proposed study is significant as to our knowledge it would be the first RCT with long-acting naltrexone in a prison population. While other investigations have reported that naltrexone is effective among parolees and probationers and pilot studies have found that it is feasible with prison inmates, the present study will focus on whether the addition of mobile XR-NTX treatment will increase adherence and thus efficacy of the medication. Finally, the importance of finding a point of equilibration will provide evidence of how many monthly XR-NTX injections will be needed. More importantly, there is a continuing need for RCTs to further examine the efficacy and effectiveness of opioid maintenance therapies within specific incarcerated populations such as prisoners because different criminal justice populations could respond to treatment differently and we could adapt treatment to work better for specific populations.⁸²

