4.0. APPROACH

4.1. Study Overview

This proposed five-year study will focus on whether the addition of mobile medical XR-NTX treatment will increase adherence and thus efficacy of the medication for pre-release prisoners. Project implementation will occur at four pre-release prisons: 1) Brockbridge Correctional Facility (BCF); 2) Dorsey Run Correctional Facility (DRCF); 3) Baltimore City Correctional Center (BCCC); 4) Maryland Correctional Institution (MCIW) for Women; 5) Central Maryland Correctional Facility (CMCF); 6) Maryland Correctional Training Center (MCTC); and 7) Roxbury Correctional Institution (see Maryland Department of Public Safety and Correctional Services **Letter of Support**). Two of these Maryland prisons were sites in our recently completed XR-NTX pilot study (see Research Strategy, above). Following initial screening, informed consent, and medical examination, consenting prisoners at each facility will be block randomized within gender, to either: (See **Figure 1** below): **XR-NTX-OTx**: One injection of XR-NTX in prison, followed by six monthly injections in the community post-

release at an opioid treatment program; or **XR-NTX+MMTx**: One injection of XR-NTX in prison, followed by six monthly injections in the community post-release at the participant's place of residence. All participants will be confirmed opiate-free by urine (all participants will receive two urine drug screens after consent) test and negative naloxone and oral naltrexone tests, and evaluated monthly for 7 months with follow up at 1-, 2-, 3-, 4-, 5-, 6-, 7- (safety visit) and 12-months after release from prison. We consider the proposed follow-up schedule advantageous from both a treatment and research perspective. Regarding treatment, it allows for quicker "rescue" for those overdue for XR-NTX injections. Concerning research, it enables us to stay in closer contact with participants and enhances post-release follow-up assessment completion rates, leading to greater generalizability of findings. The proposed study has two specific aims: **Aim 1**. To compare the two study conditions in terms of: (a) XR-NTX treatment adherence; (b) opioid use; (c) criminal activity; (d) re-arrest; (e) re-incarceration; and (f) HIV risk-behaviors (i. needle use; ii. risky sexual behaviors). **Aim 2**. To determine if the number of months of post-release XR-NTX treatment is related to outcome (a)-(f), and if so, is there a point at which XR-NTX v. Non-XR-NTX equilibrates.

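### Aim 2's equilibration interval includes month 12, when nobody has study-drug protection, so a convergence first seen after month 6 can reflect the planned stop and should not be read as the treatment length needed.

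*Combined protocol and SAP*

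**What the plan says.** **Treatment length.** The synopsis gives the duration as "7 months (1 injection in prison and 6 in the community". The clinic arm is described as "One injection of XR-NTX in prison, followed by 6 monthly injections post-release at a community opioid treatment program". In the mobile arm the prison injection is "followed by six monthly injections in the community post-release at the participant's place of residence" (section 4.1). No study XR-NTX is described after the sixth community injection in either arm.

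**Aim 2.** Section 1.2 (repeated in the synopsis, 4.1 and 5.9.1) asks first whether months of post-release treatment relate to outcomes (a) to (f). If they do, it asks: "is there a point at which XR-NTX v. Non-XR-NTX equilibrates".

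**Time points.** The Aim 2 row of Figure 2 reads "a)-(f) equilibrates Above 1-6,12 Time to relapse". Month 12 is in the interval. Month 7 is not, although Figure 2 schedules opioid use (b), criminal activity (c) and HIV risk behaviors (f) at that visit.

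**Interpretation.** Section 5.9.3 says "If we find a point of equilibration it will tell us how many months we will need to provide mobile treatment (XR-NTX". Section 3.0 says "finding a point of equilibration will provide evidence of how many monthly XR-NTX injections will be needed". The synopsis and section 1.2 say, more cautiously, that the finding could inform the length of treatment.

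**Analysis.** Section 6 contains no Aim 2 model, no definition of equilibration, no restriction to the period in which injections are offered, and no separate handling of month 12. The only treatment variable (section 6.4) is assigned arm.

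**The concern.** An equilibration point can speak to needed treatment length only if some participants are still being treated when the groups are compared. At month 12 none are. If the drug works mainly while it is active, groups that differ at month 6 will tend to look alike at month 12 whatever length is actually needed, because the schedule has ended for everyone. Read as sections 3.0 and 5.9.3 propose, that pattern could be reported as showing that about six months is enough. No participant is offered a seventh community injection, so the trial has no data that could contradict such a statement. Section 5.9.3 ties the question to the cost of the medication, so the conclusion could bear on how long treatment is funded.

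**Working it through.** The plan states no power, margin or decision rule for equilibration, so there is no figure of its own to reproduce on this point. The check is calendar arithmetic, followed by an illustration.

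**Inputs**
- Prison injection 0 to 10 days before release (5.6.1, 5.6.2).
- Interval 28 days (5.6.2, 5.7.1).
- Up to 37 days to receive the next injection (5.7.3), taken here as counted from the previous one, which fits that section's reference to days 29-37.
- Protection 37 days per injection (5.8.1).
- Month 12 taken as day 365 after release; month 7 as 7 x 30.4, about day 213.

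**Step 1: end of protection**
- On schedule: 6 x 28 = 168, less 0 to 10, puts the sixth community injection on days 158-168. Adding 37, protection ends on days 195-205.
- Every interval at 37 days: 6 x 37 = 222, less 0 to 10, gives days 212-222. Adding 37, protection ends on days 249-259.
- Prison injection only: 37, less 0 to 10, gives days 27-37.

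| Participant | Protection ends (day) | Days past it at day 365 |
|---|---|---|
| All six, 28-day intervals | 195-205 | 365 - 205 = 160 to 365 - 195 = 170 |
| All six, 37-day intervals | 249-259 | 365 - 259 = 106 to 365 - 249 = 116 |
| Prison injection only | 27-37 | 365 - 37 = 328 to 365 - 27 = 338 |

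The smallest gap is 106 days, so month 12 is off study drug for everyone. Months 1-6 (month 6 is 6 x 30.4, about day 182) fall inside the planned treatment window.

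**Step 2: month 7.** On schedule, day 213 is 213 - 205 = 8 to 213 - 195 = 18 days past protection. With 37-day intervals the sixth injection falls on days 212-222, so day 213 lies around the last dose. Month 7 is therefore post-treatment for some participants and not for others.

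**Step 3: what the stop does to an arm difference (illustration).** Suppose the effect exists only while on drug. Section 2.7.2 gives 74% v. 56% opioid-negative urines, so 26% v. 44% positive. With an assumed 20-point adherence gain in the mobile arm, the expected arm difference is 0.20 x (0.44 - 0.26) = 0.036 at each of months 1-6 and 0 at month 12. With the pilot's 0% v. 63% (2.7.3) it is 0.20 x 0.63 = 0.126, then 0. An assumed 10-point gain halves both, to 0.018 and 0.063. Moving the planned stop to 3 or 9 injections, purely to test the logic, moves the convergence to just after 3 or 9. Under this assumption it follows the schedule.

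**Step 4: simulation (illustration).** Six-injection completers (10/27, about 37%, from 2.7.3) were compared with all others: N = 216, 5,000 runs, 5% two-sided test, visits drawn independently, no carry-over. With 26% v. 44%, 76% of runs were significant at month 6 and 5% at month 12. Of the runs significant at month 6, 95% were not significant at month 12. Across 34% v. 44%, 26% v. 44% and 0% v. 63%, that share was 94-95%. It is close to 1 - 0.05 by construction, because the month-12 rates were set equal. It shows the mechanism and does not forecast how often this will happen.

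**The case against.** **No rule is stated.** A reader might infer that the plan would return a point between months 6 and 12. The documents do not support that, because equilibration is undefined and no procedure locates it. What stands is the stated interpretation, which nothing in section 6 restrains. Only one of the seven time points is affected, and a convergence within months 1-6 could not come from the planned stop, though drop-out could still cause it.

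**Aim 2 may be about months received.** On that reading, month 12 compares people with shorter and longer past exposure, which is a fair question about durability. The plan does not say that this is meant, its operational definition (time to relapse) does not settle it, and exposure would still be capped at six community injections.

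**Cause.** A reader might infer that any convergence after month 6 must be due to withdrawal. That goes too far. Lasting benefit would weaken the effect, non-study XR-NTX is neither planned nor excluded, and other causes are possible.

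**Gap between visits.** A reader might infer that nothing between months 6 and 12 can be dated. That is wrong for several outcomes. Section 5.8.2 has opioid use and crime collected over the whole follow-up, with timeline follow-back (TLFB), and re-arrest and re-incarceration are time-to-event outcomes from official records. The difficulty is mainly with urine screens and perhaps risk-behavior scores.

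**Hedging.** The synopsis and 1.2 are cautious, and 5.9.3 says firm conjectures are difficult. That last remark concerns predicting the answer. It does not qualify how an equilibration point will be read. Aim 2 has no hypothesis of its own, and the Aim 1 comparison of arms is untouched.

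**Conclusion.** The point holds in this form: month 12 lies at least 106 days beyond any study-drug protection, so a convergence first seen after month 6 can reflect the planned stop, and the design cannot show a needed length above six community injections. The 170-day figure is an upper limit only for those who received all six community injections; those who stopped early have been off drug longer.

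The conclusion rests on the protocol's 28-day and 37-day figures, on no study dosing after the sixth community injection, and on limited carry-over. It is a point about interpretation and is worth correcting because the correction needs only wording. It does not show that six injections are too few or too many.

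**What to change.** 1. For the repeatedly measured outcomes (b, c, f), base any equilibration or needed-length statement on months 1-6 only. If there is no convergence by then, report it as not reached within six injections and claim no needed length.
2. Show months 7 and 12 separately as the course after the planned end of treatment. Month 7 is already collected for b, c and f. Classify it by each participant's actual last injection date, since with delayed injections it can still be on drug.
3. Where TLFB gives dated opioid use and crime, use those dates.
4. Keep re-arrest and re-incarceration, which Figure 2 lists only at month 12, as time-to-event outcomes over 12 months related to months of treatment received. Do not read an equilibration point from them. A blanket limit to months 1-6 would remove their only listed time point.
5. Amend the Aim 2 row of Figure 2, sections 3.0 and 5.9.3, and the matching aim text in the synopsis and 1.2, so that convergence after month 6 is not read as the treatment length needed.

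**Cost.** Wording, plus deriving last injection dates from the clinic records already used for adherence (5.8.1). There are no new visits or data and no change to treatment. The downside is that Aim 2 may end with not reached instead of a number.

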6.0. Statistical Analyses

6.1. Guiding Principle. Although the description of the statistical approach that follows is more in line with the language associated with a ‘traditional’ superiority trial, we endorse the “sensible formulation of the significance test” proposed by Jones and Tukey.⁹⁷ These authors outline an approach to significance testing that focuses not on the rejection of a null hypothesis, but on determining whether the data favor a determination of superiority or inferiority. As part of their approach, they suggest reporting not only a test statistic and its associated probability value but also a confidence interval and an effect size related to the determination of any difference. It would be our intention in reporting our results to adhere to Jones and Tukey’s suggestions.

6.2. Intent-to-Treat Approach. All analyses will be conducted on available study-related data from all participants, regardless of whether or when they drop out of treatment; i.e., the intent-to-treat population is all persons consented and randomized to the study.

6.3. Outcome Measures. Except for criminal justice records, collected at study conclusion, outcome data will have been collected monthly during the project: at baseline (study entry), and at 1, 2, 3, 4, 5, 6, 7, and 12 months following release from prison (see **Figure 2**, above). The resulting dependent variables will be of three distinct types: 1) continuous random variables (e.g., RAB scale scores), assumed to follow a normal distribution; 2) discrete random variables (e.g., number of days of criminal activity), assumed to follow a Poisson distribution; and, 3) dichotomous variables (e.g., treatment adherence, urine drug screening results), assumed to follow a binomial distribution. [All distributional assumptions will be evaluated prior to the conduct of all analyses, and if such assumptions are not met, assumptions will be modified and statistical methods chosen accordingly, and/or outcome measures transformed appropriately. For example, it may be necessary to allow for under- or over-dispersion in the logistic and Poisson regression analyses, or use zero-inflated Poisson or negative binomial models rather than a Poisson model for the count variables.]

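### Aim 2 converts a 'point of equilibration' into months of treatment needed, but the planned analyses can show a difference and cannot show that groups have become equal

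*Combined protocol and SAP*

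**What the plan says.** Aim 2 (sections 1.2, 4.1 and 5.9.1) asks whether months of post-release treatment are related to outcomes (a)-(f), "and if so, is there a point at which XR-NTX v. Non-XR-NTX equilibrates". Section 5.9.3 draws the practical conclusion: "If we find a point of equilibration it will tell us how many months we will need to provide mobile treatment (XR-NTX". Section 3.0 likewise presents an equilibration point as evidence on the number of injections.

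On inference, section 6.1 adopts an approach that "focuses not on the rejection of a null hypothesis, but on determining whether the data favor a determination of superiority or inferiority", and promises "a confidence interval and an effect size related to the determination of any difference". Section 6.5 uses a generalized linear mixed model for every analysis, and section 6.4 names one treatment variable, the randomised condition. Section 6 does not define equilibration and gives no margin and no rule for locating a month.

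The only operational definition is in the Aim 2 row of Figure 2. For all of (a)-(f), at months 1-6 and 12, it reads "Time to relapse".

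**The concern.** Equilibration means that two groups which differed no longer do. A framework that decides between superiority and inferiority has three possible results: better, worse, or not determined. None of them is equal. Without a margin, a confidence interval that includes zero cannot be told apart from convergence, and monthly comparisons at this sample size will often include zero while a real difference persists.

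The Figure 2 definition does not fill the gap. Time to relapse is at best a measure of opioid use. It is one event time per person, so it gives no month-by-month difference, and it says nothing about when crime, arrest, incarceration or HIV risk converge.

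At stake is the claim in 5.9.3 and 3.0. Lack of precision in some month could be reported as the point beyond which treatment, or mobile delivery, adds nothing.

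**Working it through.** **Inputs.** N=216 and alpha .05 (section 6.7; two-sided assumed). Difference of .2 SD: the small effect used in 6.7 for normal outcomes, borrowed here because Aim 2 states none. Shares injected at community months 1-6 in the pilot: 21, 18, 13, 11, 10 and 10 of 27 (section 2.7.3). Between-month correlation: 6.7 names structures but gives no values, so .3 to .9 is assumed (exchangeable).

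**The plan's own figure.** For f²=.037 with N=216 and one degree of freedom, the noncentrality is .037 × 216 = 7.99 and power is .80, as section 6.7 states. For two equal groups this is d = 2√.037 = .38 SD. One look therefore has 80% power only for a difference nearly twice .2 SD. The simulated power of .81-.85 cannot be reproduced, because SDs and correlations are not given.

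**One month.** SE (in SD units) = √[1/(216p) + 1/(216(1−p))]. The half-width is 1.96 × SE. The probability of non-significance is Φ(1.96 − .2/SE) − Φ(−1.96 − .2/SE).

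| Month | p | SE | 95% half-width | P(non-significant) |
|---|---|---|---|---|
| 1 | .78 | .164 | .32 | .77 |
| 2 | .67 | .144 | .28 | .72 |
| 3 | .48 | .136 | .27 | .69 |
| 4 | .41 | .139 | .27 | .70 |
| 5 | .37 | .141 | .28 | .71 |
| 6 | .37 | .141 | .28 | .71 |

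With the randomised arms instead (108 v. 108, the mobile contrast of 5.9.3), SE = √(2/108) = .136, the half-width is .27 and the probability is .69. With 120 per arm these are .25 and .66.

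**Six months together.** Multivariate normal simulation with a constant .2 SD difference; each cell gives pilot shares / randomised arms.

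| Correlation | Any of six months non-significant | Significant earlier, non-significant at month 6 |
|---|---|---|
| .3 | .99 / .98 | .45 / .46 |
| .5 | .96 / .95 | .36 / .37 |
| .7 | .92 / .90 | .27 / .28 |
| .85 | .87 / .85 | .18 / .19 |
| .9 | .84 / .82 | .14 / .15 |

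Non-significance at month 6, whatever came before, has probability about .70 at any correlation. If one first requires a significant overall effect (seven looks, 108 per arm), at least one non-significant look follows in 92%, 79% and 59% of such trials at correlations .5, .7 and .85.

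**Could equality be shown?** A 95% CI with half-width .27 or more cannot lie inside ±.2 SD, even if the observed difference is exactly zero. With 108 per arm and a true difference of zero, two one-sided tests at .05 have power 0% at a margin of .2 SD, 42% at .3 and 80% at .4. With the stricter 95% CI, power at .4 SD is 2Φ(.4/.136 − 1.96) − 1, about 67%. These figures are for one outcome in one month, unadjusted.

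**The case against.** The strongest reply is that the plan nowhere says a non-significant month counts as equilibration. Section 6.1 commits to intervals and effect sizes, section 6.4.3 looks at course over time, and Aim 2 is conditional on a relation with months of treatment, so an estimated plateau is another possible reading. The authors also hedge: 1.2 calls the finding only potentially important, and 5.9.3 admits that firm conjectures are difficult.

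Much of this stands. A reader might infer that the plan would declare false equilibration in over 90% of trials. The documents do not support that. The figure needs the any-one-month rule and a correlation up to about .7; at .85-.9 it is 82-87%. It also counts trials with no significant month at all, where there was nothing to converge. Under the more natural sequence, a difference followed by none at month 6, the range is 14-46%. A reader might also infer that non-significance is the only route to equilibration under the plan, and the promised intervals make that too strong.

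The inputs are borrowed too: the pilot shares come from 27 people in one arm, N=216 is the 12-month number applied to months 1-6, and .2 SD belongs to the randomised comparison.

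What the reply does not answer is that the intervals have no margin against which to be read, while 5.9.3 says without qualification what an equilibration point will tell.

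**Conclusion.** The point holds as a mismatch between claim and method. Sections 5.9.3 and 3.0 make a duration claim that the stated analyses cannot support, and the one operational definition does not measure convergence for most of the outcomes it covers. Both follow from the text and do not depend on any simulated rate.

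On size, under N=216 and a constant .2 SD difference, a real difference is missed in a single month about 7 times in 10 (.69-.77 with pilot shares, .69 with randomised arms), and the monthly interval is too wide to exclude that same difference. How often a whole trial would appear to equilibrate depends on a rule the plan does not give: about 82-99% if any one of six months suffices, about 70% on month 6 alone, and 14-46% if an earlier significant month is required.

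The randomised comparison in Aim 1 is not affected. The change should be made, but it concerns the second aim and its wording.

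**What to change.** 1. In 5.9.3, 3.0 and section 6, state that a non-significant difference is not equilibration.
2. In section 6, add that Aim 2 reports differences with 95% CIs at months 1-6 and 12 for the repeatedly measured outcomes: opioid use, days of crime and HIV risk.
3. Allow a months-needed statement only if the CI at that month and at every later listed assessment lies inside a margin stated in advance on that outcome's scale. Otherwise report 'not determined'.
4. State that a margin of .2 SD cannot be met month by month at N=216 with unadjusted comparisons.
5. In the Aim 2 row of Figure 2, replace time to relapse with the Aim 1 measures of those three outcomes. Keep time-to-event for re-arrest and re-incarceration without a monthly equilibration claim, since records are collected once, at month 12. Drop adherence from the equilibration contrast: comparing injected with non-injected participants on injections received is circular.

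The cost is a paragraph of analysis text, two edited sentences and one table row, with no new data. The downside is that Aim 2 will often end as 'not determined'.
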